#### 4.1.3 Endpoints for the ancillary studies

- Ancillary study 1
  - Primary outcome measure: plasma citrulline level at H72
  - Secondary outcome measures: SOFA score; plasma levels of citrulline and I-FABP on D0, D3, and D8; proportion of patients whose plasma I-FABP is  $\geq 100 \text{ pg/mL}$  on D0, D3, and D8; proportion of patients whose plasma citrulline is  $\leq 10 \mu\text{L/L}$  on D0, D3, and D8; mean plasma I-FABP; mean plasma citrulline; proportion of patients with at least one episode of bacteremia; proportion of patients with at least one episode of gastrointestinal intolerance; proportion of patients with at least one episode of diarrhea; in the enteral-nutrition group, cumulative calorie intake over the first 3 days and on D7; impossibility of administering enteral nutrition.
- Ancillary study 2

---

- Primary outcome measure: proportion of patients with abundant microaspiration
- Secondary outcome measures: salivary amylase levels in tracheal aspirates

## 5.14 Description of the research project methodology with a study diagram including scheduled visits and investigations

### 4.2.1 Study design

This multicenter randomized controlled open trial will compare two parallel groups of patients receiving mechanical ventilation and vasoactive amine therapy and given early nutritional support according to one of two strategies (first-line enteral nutrition versus first-line parenteral nutrition) at the acute phase of ICU management (D1 to D7).

### 4.2.2 Conduct of the study

#### 4.2.2.1 Inclusion

Patients will be included in the study within 24 h after intubation, or within 24 h after ICU admission if they were intubated before ICU admission. Study inclusion will occur after the usual initial life-sustaining interventions required in patients with shock managed using ventilatory support. The study will include patients requiring vasoactive amine therapy after volume expansion if indicated and any evaluation procedures dictated by the clinical condition. These initial treatment and evaluation decisions will be at the discretion of the physician in charge of each patient, who will follow standard procedures in the relevant study ICU.

Information about the study and collection of consent to study participation will involve the patient if he or she is conscious and the next of kin otherwise. If informed consent is obtained from the next of kin, informed consent will be sought from the patient as soon as he or she recovers a sufficient level of consciousness.

A log of patients considered for study participation will be kept and will include any reasons for non-inclusion and refusals of consent.

---

After checking the inclusion and non-inclusion criteria, as well as consent to participation given by the patient or next of kin, the investigator will be able to include the patient. At inclusion, demographic data, patient characteristics, and vital signs will be collected: date of birth, sex, date of ICU admission, reason for ICU admission, McCabe and Knaus scores, chronic co-morbidities, body weight, height, BMI, SOFA score, and SAPS II.

#### 4.2.3 Nutritional support protocol

The nutritional support protocol, including measures designed to evaluate tolerance, will be standardized as indicated below.

##### a. General principles

Nutritional support will be started as soon as possible after the initiation of invasive mechanical ventilation and no later than 24 hours after intubation or after ICU admission in patients intubated before ICU admission.

The calorie target for each patient will be estimated based on body weight as 20-25 Kcal/Kg/day during the acute phase (7 days at the most) then 25-30 Kcal/Kg/day from day 7 to extubation. In obese patients (BMI > 30 Kg/m^2), the body weight yielding a BMI of 30 will be used to estimate the calorie target.

Nutritional support will be prescribed as a flow rate (mL/hour) and started at the prescribed flow rate (as opposed to increased gradually). The feed will be delivered continuously, over the 24-hour cycle, with no interruptions. Actual feed delivery will be monitored regularly based on the volumes delivered relative to the predefined daily calorie targets. In addition, special attention will be directed to avoiding delays. Any interruption in feed delivery will be reported to the ICU physician in charge. Except in special situations, nutritional support will not be interrupted while transporting the patient. However, when enteral or parenteral nutrition must be interrupted (e.g., for a specific gastrointestinal or radiological investigation), the flow rate will not be increased to compensate for the interruption. Finally, the patient will be in the semi-recumbent supine position with the torso at 30° to 45° from the horizontal plane.

##### b. Enteral nutrition

Isoosmotic isocaloric normal-protein polymeric preparations will be used during the first week, after which the choice of feed will be at the discretion of the physician. The enteral nutrition preparation will be delivered continuously, over the 24-hour cycle, with no

---

interruptions, via a 14-French silicone gastric tube. Tube position in the middle of the stomach will be checked on a radiograph obtained at ICU admission or immediately after tube placement, as well as when the tube is changed or repositioned. Special attention will be directed to the risk of tube obstruction, particularly when administering medications: the tube will be flushed regularly with 20-30 mL of water.

A predefined protocol will be used to manage upper gastrointestinal intolerance to enteral nutrition (Appendix 1) (71). The tolerance of enteral nutrition will be monitored based only on episodes of significant vomiting or regurgitation (passage of enteral nutrition formula into the mouth, outside the mouth, or into the endotracheal tube in the absence of care procedures or mobilization). The residual gastric volume will not be monitored. Intolerance to enteral nutrition will be defined as the presence of significant vomiting or regurgitation. Minimal regurgitation or vomiting triggered by tracheal aspiration or oral cavity care will not be taken to indicate intolerance. Intolerance to enteral nutrition will lead to the following two measures:

- First, initiation of treatment with a prokinetic agent *after confirmation that there are no contraindications and after obtaining a prescription by a physician*. The study ICUs will use the prokinetic agent of their choice, according to their standard practice. The prokinetic agent will be continued until enteral nutrition at the highest prescribed flow rate has been well tolerated for 48 hours. The prokinetic agent will then be discontinued.
- Second, if the intolerance persists despite prokinetic therapy, the flow rate will be decreased by 25 mL/h, every 6 hours, until the signs of intolerance resolve. Therefore, enteral nutrition will be stopped (and the gastric tube placed under suction) only in patients with intolerance despite a flow rate  $\leq 25$  mL/h. All interruptions in enteral nutrition delivery must be reported to the intensivist in charge. This precaution is particularly important in patients receiving insulin. Enteral nutrition will be resumed at the prescribed flow rate (appropriate to the patient's needs) after 6 hours have elapsed with no further signs of intolerance. (71).

### c. Parenteral nutrition

Ternary admixtures packaged in bags and containing the three groups of macronutrients will be used according to standard practice in each participating center. Supplemental electrolytes will be supplied in a solution separate from the parenteral feed, according to the needs of each patient. Parenteral nutrition will be delivered continuously, over the 24-hour

---

cycle, with no interruptions, via a central venous catheter (CVC). Special attention will be directed to preventing infections by complying with the standard protocols for CVC insertion and maintenance used in each of the participating centers. Proper positioning of the CVC will be checked using a radiograph.

**d. Additional intakes (water, electrolytes, trace elements, and vitamins)**

Additional water and electrolytes will be given intravenously according to the needs of each individual patient as assessed by the physician in charge and in compliance with standard practice in each study ICU.

Intravenous vitamins, trace elements and, when appropriate, will be given according to the needs of each individual patient, using the standard preparations and protocols available in each study ICU.

These components will not be added to the parenteral nutrition bags. Instead, they will be given using a separate intravenous bag and line, continuously over the 24-hour cycle; if needed, this separate preparation will be shielded from light using aluminum foil.

#### 4.2.4 Study intervention: first-line enteral or parenteral nutrition

After study inclusion, patients will be allocated at random to one of two nutritional-support strategies (Figure 1).

[figure not shown]
**In the parenteral-nutrition group (P group),** the patients will receive first-line parenteral nutrition for at least 72 hours. After these 72 hours, the course of action will depend on the results of the daily hemodynamic status evaluation. If the hemodynamic condition is stable (no vasoactive amines for 24 consecutive hours and arterial lactic acid level below 2 mmol/L) and the enteral route can be used, parenteral nutrition will be stopped and immediately replaced by enteral nutrition at the flow rate needed to achieve the previously defined calorie target. If on the contrary the patient still requires vasoactive amine therapy and/or the arterial lactic acid level is equal to or greater than 2 mmol/L, parenteral nutrition will be continued for a total of 7 days (168 hours). On day 8, in the absence of contraindications to enteral nutrition, parenteral nutrition will be stopped and enteral nutrition started. Supplemental parenteral nutrition may be added subsequently in the event of intolerance to enteral nutrition precluding the achievement of the predefined calorie targets.

**In the enteral-nutrition group (E group),** the patients will receive first-line enteral nutrition. In the event of persistent gastrointestinal intolerance precluding achievement of the

---

predefined calorie targets, supplemental parenteral nutrition may be added starting on day 8 in compliance with North-American recommendations and with the recently published study by Casaer (6, 72). Isoosmotic isocaloric normal-protein polymeric preparations will be used during the first week, after which the choice of the preparation will be at the discretion of the physician. To minimize the risk of gastric intolerance and consequently of vomiting, the volume of supplemental water given enterally will be as small as possible during the first study week.

Figure 1: Protocol

---

#### 4.2.5 Monitoring of intestinal transit

The volume and appearance of the stools will be monitored daily.

The occurrence of constipation (no stool for more than 6 days) or diarrhea (more than 300 mL of liquid stool or 4 loose stools per day) will be reported and will lead to the appropriate diagnostic and therapeutic management (Appendix 2) (15, 73, 74).

#### 4.2.6 Special situations

- Patients in the prone position: intolerance to enteral nutrition is particularly common in this position and will be prevented via prophylactic prokinetic treatment started at the first turn in the prone position (75, 76).
- Patients receiving insulin therapy: very close monitoring and strict application of the insulin-therapy protocol used in each study-center institution are crucial. Blood glucose targets will be at the discretion of each study center according to their usual practice and protocols. In addition,
  - in the event of a decrease in the enteral feed flow rate due to poor tolerance of enteral nutrition (regurgitations), blood glucose levels will be determined at least hourly during the first 2 hours following the flow rate reduction; if blood glucose levels remain stable, the patient will be returned to the frequency of monitoring specified in the insulin-therapy protocol;
  - In the event nutritional support is discontinued, blood glucose levels will be determined hourly for as long as the patient remains off enteral nutrition.
- Patients who are re-intubated or re-admitted to the ICU: if this event occurs at the acute management phase (<7 days after first use of mechanical ventilation), the patient will be managed in the same way as during the first period of intubation, until the end of the acute phase. Thus, a patient allocated at random to the enteral-nutrition group (E group) will remain in this group for at least the first 7 days of management. If the event occurs after the end of the acute phase, the method of nutritional support will be at the discretion of the physician in charge.

#### 4.2.7 Patient follow-up

The following will be recorded until the patient is extubated: vital signs, nutrition monitoring data, laboratory tests, and data relevant to nosocomial infections. The patient will

be followed-up to hospital discharge, D28, and D90. At these time points, vital status will be recorded. Below is a flowchart of patient follow-up.

	Inclu-sion	Rando-mization	D0*	D1 to Dn	End of study	D28	D90
Eligibility: check inclusion and exclusion criteria	X						
Patient information and consent	X						
Randomization	X						
Demographics	X						
Characteristics			X				
Ventilation			X				
Laboratory tests			X	X*			
SOFA			X	X			
Nutritional evaluation			X	X			
Treatments used			X	X			
Daily calorie intake				X			
Nosocomial infections					X		
Final extubation						X	
Final discontinuation of nutritional support						X	
Survived / died					X	X	X

\*from time at inclusion to 11:59 pm

---

Design of the ancillary studies

---

### Ancillary study 1

The plasma citrulline and I-FABP assays on D0, D3, and D8 will be performed using blood drawn as part of the standard care of critically ill patients; the volume of each blood sample will be increased slightly (by about 2 mL) to allow these assays. For amino acid chromatography, blood will be drawn in a lithium heparin tube, which will be transported on ice as promptly as possible to the medical biochemistry laboratory. At arrival at the laboratory and within 2 hours after blood collection, the sample will be centrifuged (4°C, 1900 rpm, 10 minutes) and the plasma stored at -70 °C until the analysis.

The samples will be centralized at the Biology Center of the Besançon Teaching Hospital. After thawing and deproteinization, ion-exchange chromatography will be performed on a Hitachi L-8800 analyzer (Hitachi, Tokyo, Japan).

I-FABP will be assayed using a blood sample drawn into an EDTA tube, which will be taken as rapidly as possible to the medical biochemistry laboratory. At arrival at the laboratory, the sample will be centrifuged (4°C, 1500 rpm, 15 minutes) and the plasma stored at -70°C until analysis by ELISA (Hycult Biotech, Uden, The Netherlands) at the Biology Center of the Besançon Teaching Hospital.

### Ancillary study 2

Tracheal aspiration will be performed according to standard practice in the study centers. All tracheal aspirates obtained within 48 hours after randomization for the NUTRIREA2 trial will be stored frozen at each study center. The frozen aspirates will be sent to the Biochemistry Department of the Lille Teaching Hospital (Dr. [name], Dr. [name], and Dr. [name]), where the pepsin and salivary amylase assays will be performed.

The measures taken to prevent microaspiration will comply with current recommendations and with standard practice in each study center. They will consist of the following:

- Endotracheal tube cuff pressure kept at about 25 cm H2O;
- Semi-recumbent patient position;
- Application of at least 5 cmH2O of positive end-expiratory pressure (PEP) in patients without contraindications;
- Daily evaluation of criteria for weaning off mechanical ventilation, to minimize the duration of mechanical ventilation;
- No routine prophylactic treatment of stress-induced ulcers; and
- Limited use of sedation and application of a sedation management protocol.

---

5.15 4.3 Description of measures taken to minimize and avoid biases

4.3.1 Random allocation

The randomization scheme will be stratified on the study site. Patient category (postoperative or medical) will not be used for stratification, as the distribution between postoperative and medical patients is expected to be heavily skewed (based on earlier studies, surgical patients are expected to contribute only 10% of the study population). Random allocation will be performed using the electronic case-report form available at each study center.

4.3.2 Blinding methods

The trial will be open, since nutritional support requires the intervention of a nurse and involves two different routes of administration (enteral or parenteral), one for each group of study patients.

Given the absence of blinding, the secondary endpoints relevant to nosocomial infections will be validated by an adjudication committee. Nosocomial infections are of the utmost clinical importance, and the results of our study may have a major impact on future patient management. Consequently, a very high level of uniformity in data collection is crucial to ensure that highly reliable results are obtained.

4.4 Expected duration of study patient participation and description of the time sequence and duration of all trial periods, including follow-up, where applicable

The duration of participation of each patient in the study will depend on the time to extubation. The vital status of each patient will be recorded at ICU discharge, at hospital discharge, on D28, and on D90. For patients discharged before D28 and/or D90, a telephone interview will be arranged.

Study recruitment is expected to last 30 months, yielding a total patient follow-up time of 36 months.

4.5 Reasons for permanent or temporary study discontinuation

#### 4.5.1 Patient withdrawal from the study

The patients or next of kin may ask to withdraw from the study at any time and for any reason. In the event of secondary withdrawal of consent to participation in the research project, none of the data collected since study inclusion of the patient will be used, in compliance with the wishes of the patient or next of kin. Withdrawal of a patient from the study will have no impact on the standard care delivered to the patient for the condition that prompted the hospital admission. The laboratory tests specific to the study nutritional-support protocol will not be performed. All investigations and treatment decisions will be at the discretion of the physician in charge of the patient.

Should a patient be lost to follow-up, all data for that patient collected since study inclusion will be used, and the investigator will make every effort to contact the patient.

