STRATEGIES / PROCEDURES SPECIFIC OF THE ANCILLARY STUDIES	
 
– Ancillary study 1 The assays on D0, D3, and D8 will be performed on part of the blood samples drawn for the standard care of these critically ill patients.
 
– Ancillary study 2 All tracheal aspirates (obtained routinely in patients receiving invasive mechanical ventilation) will be collected over the first 48 hours following randomization and stored at -20°. The aspirates will then be centralized at the Biology and Pathology Center of the Lille Teaching Hospital (Lille, France), where they will be used for quantitative assays of pepsin and salivary amylase.
 

NUMBER OF PATIENTS	1427 in each group, i.e., 2854 patients in all
NUMBER OF PATIENTS IN THE ANCILLARY STUDIES	
 
– Ancillary study 1 85 patients per group, i.e., 170 patients in all
 
– Ancillary study 2 94 patients per group, i.e., 188 patients in all
 

DURATION OF THE STUDY	
Inclusion period duration: 30 months
 
Duration of participation for each patient: duration of mechanical ventilation (final extubation), follow-up until hospital discharge
 
Total study duration: 36 months (30 months for inclusion plus 6 months for follow-up and data checking).

PLANNED TRIAL START DATE	September 3, 2012
EXPECTED IMPACT	If the study hypothesis is confirmed, early enteral nutrition will become the reference standard for initial nutritional support in mechanically ventilated patients with shock, and the result will be decreased morbidity and mortality rates and improved overall patient outcomes.

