#### 7.1.3 Analysis of the primary endpoint

Day-28 mortality will be reported as the point estimate with the 95% confidence interval in each group. Day-28 mortality will be compared between the two groups using the chi-square test.

---

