## 7.2 Estimated sample size, and estimated numbers of patients recruited at each study center, with supporting statistical information

This clinical randomized controlled superiority trial will seek to demonstrate that the D28 mortality rate in patients admitted to the ICU and treated with mechanical ventilation and vasoactive amines is lower in patients given early enteral nutrition than in patients given early parenteral nutrition. Assuming a 37% D28 mortality rate in the parenteral-nutrition group and a 5% decrease in mortality with early enteral nutrition (i.e., a D28 mortality rate of 32%), with the alpha risk set at 4.9% and the beta risk at 20%, 1427 patients are needed in each group (Newcombe, Statist Med 1998; 17:873-890), i.e., a theoretical total of 2854 patients.

The mortality rates used for the sample size estimation are those obtained in the NUTRIREA-1 randomized controlled trial in nine centers (CRICS network), in which similar inclusion criteria were used.

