## 7.5 Handling of missing, unused, or invalid data

In this study, patients from whom consent to the study was not obtained and those who secondarily withdrew their consent will not be included in the analyses. Apart from these two situations, the likelihood that patients will be lost to follow-up is small. The study patients will be admitted to ICUs, and the primary endpoint is objective (D28 mortality). However, should there be any patients for whom information on the primary endpoint is missing, then these patients would be considered as having died before D28, in both randomized arms.

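### Withdrawal of consent erases even a known day-28 outcome, so entry to the primary analysis can depend on survival; the comparison is biased only if deletion also differs by arm

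*Combined protocol and SAP*

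**What the plan says.** Section 4.5.1 lets the patient or the next of kin withdraw at any time, without giving a reason. After that, "none of the data collected since study inclusion of the patient will be used". Section 7.5 carries this into the analysis: "those who secondarily withdrew their consent will not be included in the analyses". It also drops patients for whom consent was never obtained.

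Section 4.2.2.1 allows the next of kin to consent when the patient is not conscious. In that case "informed consent will be sought from the patient as soon as he or she recovers a sufficient level of consciousness".

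Sections 7.1.2 and 7.7 state an intention-to-treat analysis, and 7.1.2 keeps every patient in the assigned group whatever happens afterwards. The primary analysis is simple: "Day-28 mortality will be compared between the two groups using the chi-square test". Other missing day-28 outcomes are treated in the opposite way to withdrawals: under 7.5 the patient stays in the analysis and is counted as dead.

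The plan gives no expected withdrawal rate, no way to stop study procedures while keeping vital status, no report of deletions by arm and no sensitivity analysis for them.

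**The concern.** The trial enrols ventilated patients in shock within 24 hours of intubation, or of ICU admission if they were intubated earlier, so many can be expected to enter on next-of-kin consent. A patient who dies without waking never reaches the second consent decision. A patient who wakes does, and a refusal or withdrawal then removes the whole record. There is no time limit, so even a day-28 outcome already recorded can be lost. Whether a patient is in the primary analysis set can therefore depend on the primary endpoint, which contradicts the intention-to-treat statement.

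Two things are at stake. If survivors are deleted more often than deaths, each arm's day-28 mortality is overstated. If, in addition, the deletion rate differs between arms, the treatment difference is distorted, and nothing in the plan would reveal it.

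**Working it through.** **Inputs from the plan (section 7.2).** "Assuming a 37% D28 mortality rate in the parenteral-nutrition group and a 5% decrease in mortality with early enteral nutrition", so 37% versus 32%; "with the alpha risk set at 4.9% and the beta risk at 20%, 1427 patients are needed in each group".

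**Reproducing the plan's figure.** Two-sided test of two proportions, pooled variance under the null, no continuity correction, mean mortality (0.37 + 0.32)/2 = 0.345:

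n = [1.9686 × √(2 × 0.345 × 0.655) + 0.8416 × √(0.37 × 0.63 + 0.32 × 0.68)]² / 0.05² = 1426.5, rounded up to 1427 per arm.

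This matches and gives 80.0% power. The figure assumes that every randomised patient is analysed.

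**Effect of deletion on one arm.** Let p be true day-28 mortality, and let ws and wd be the shares of survivors and of deaths that are deleted. Observed mortality is

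p(1 − wd) / [p(1 − wd) + (1 − p)(1 − ws)].

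The documents give neither share, so every ws and wd below is an assumption.

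**Equal deletion in both arms, true rates 37% and 32%:**

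| ws | wd | Parenteral | Enteral | Difference (points) |
|---|---|---|---|---|
| 1% | 0 | 37.23% | 32.22% | 5.02 |
| 5% | 0 | 38.20% | 33.13% | 5.08 |
| 3% | 1% | 37.48% | 32.45% | 5.03 |
| 3% | 3% | 37.00% | 32.00% | 5.00 |
| 1% | 3% | 36.53% | 31.56% | 4.97 |

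Deletion that favours survivors moves both rates up and hardly moves the difference. With 5% of survivors deleted in each arm, power is 79.3%. When the true rates are equal, Type I error stays at 4.9%.

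**Unequal deletion, no true effect (34.5% in both arms), survivors only (wd = 0).** Type I error is approximately Φ(d/SE − 1.9686) + Φ(−d/SE − 1.9686), where d is the spurious difference.

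- 1% enteral, 3% parenteral: about 9 and 28 patients deleted. Observed 34.73% and 35.19%, d = 0.46 points, SE = 1.797 points, d/SE = 0.258. Type I error = 0.0436 + 0.0130 = 5.7%.
- 2% and 5%: about 19 and 47 deleted. Observed 34.96% and 35.67%, d = 0.71 points, SE = 1.810 points, d/SE = 0.392. Type I error = 0.0575 + 0.0091 = 6.7%.

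**Unequal deletion with the planned effect.** Deleting 2% of enteral and 5% of parenteral survivors shows 38.20% − 32.44% = 5.76 points. The reverse shows 37.47% − 33.13%, or 4.35 points before rounding of the rates.

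**How far deletion would lean towards survivors.** At 34.5% mortality, 65.5% of deleted patients would be survivors even if deletion ignored outcome, and this causes no bias. If survivors withdraw at twice the rate of deaths, the share is 0.655 × 2 / (0.655 × 2 + 0.345) = 79%; at three times the rate, 85%. The documents do not fix this ratio.

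**The case against.** A reader might infer that deletion is confined to survivors. The documents do not support that. Under 4.5.1 the next of kin may withdraw at any time, including the first days when the patient is unconscious, so patients who later die can be deleted. Regaining consciousness is also not the same as surviving to day 28: a patient can wake, refuse and then die. If both outcomes are deleted at equal rates, nothing is biased. This objection stands, and it makes survivor-selective deletion a likelihood of unknown size.

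A reader might also infer that the treatment contrast is biased and that the Type I error exceeds 4.9%. That needs deletion to differ by arm. Section 4.3.2 says only that the trial is open; it does not say that patients asked after recovery know or care which route they had. Sections 4.2.4 and 6.1 move stable parenteral patients to enteral feeding after 72 hours, and the others on day 8 if there is no contraindication, so many of those asked may by then be fed the same way in both arms. The imbalances assumed above are large for their size, and a count of exclusions by arm would expose them. This stands as well, except that the plan asks for no such count.

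Finally, 4.5.1 presents deletion as respecting what the patient or family want, and the ethics committee approved the trial. That is fair, but the section does not provide for asking. It takes a wish to leave the study as a wish to erase what has been collected.

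**Conclusion.** The point holds as a conflict within the plan and a cheap improvement, not as a demonstrated bias. Sections 4.5.1 and 7.5 remove patients, some with known outcomes, from an analysis that 7.1.2 calls intention-to-treat, and the consent sequence in 4.2.2.1 gives a reason to expect more removals among survivors.

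Under assumed survivor-only deletion the effect on the comparison is zero under the null when rates are equal. It is 0.46 to 0.71 points, with Type I error of about 5.7% to 6.7%, at 1% versus 3% and 2% versus 5%. Against a 5-point target this is modest. If some deaths are deleted too, it is smaller still. These figures rest on assumed withdrawal rates and an assumed difference between arms, neither of which the documents supply.

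**What to change.** In 4.5.1, 7.5 and the information sheet, separate stopping study procedures from refusing use of data. At withdrawal or refusal, ask the patient or next of kin whether data already collected and day-28 and day-90 vital status may be kept, and delete only if that is refused.

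Report the number deleted by arm and by who withdrew. Add a sensitivity analysis of day-28 mortality with all randomised patients in the denominator and four settings for the deleted patients: all alive, all dead, and the two extremes that are opposite by arm. It needs only the counts randomised and deleted per arm, so it uses no clinical data from anyone who refused. Counting all deleted patients as alive would not do alone: it assumes that each one survived, while 7.5 counts other missing outcomes as dead.

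The cost is wording, one extra question at withdrawal and a little more analysis. Section 7.6 finalises the analysis plan at database lock, so the analysis can still be added before then. Some patients will still refuse, and the bounds widen with their number: their range is (deleted enteral + deleted parenteral)/1427, or (9 + 28)/1427 = 2.6 points and (19 + 47)/1427 = 4.6 points in the two scenarios above. Asking permission to keep vital status is therefore the more valuable half of the change.
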